Type 2 diabetes (T2D) is a global health problem affecting more than 370 million people worldwide. According to the estimations of the International Diabetes Federation, Bosnia and Herzegovina has one of the highest prevalence of diabetes in Europe, 12.3%.¹ Despite development of novel pharmacological agents, sulfonylureas (SUs) remain the most commonly prescribed drugs after metformin in the treatment of T2D, because of their high efficacy, extensive experience and least cost.² Due to their low cost compared to some of the newer agents, SUs are particularly widely used in low and middle income countries, where they have been recommended as treatment of choice for T2D.³ The most common and potentially most serious adverse effect of sulfonylurea therapy is hypoglycaemia.⁴ Severe hypoglycaemia may result in significant morbidity, including higher risk of dementia, stroke and mortality.⁵⁻⁷ Among different SUs, gliclazide has been recommended as a first choice in many countries, as it seems to be associated with lower risk of hypoglycaemia and lower morbidity and mortality compared with other SUs.^{8,9} Furthermore, gliclazide has been included on the WHO Model List of Essential Medicines, based on safety data in elderly patients. Nevertheless, in a recent population-based cohort study, gliclazide showed a similar risk of hypoglycaemia compared with other SUs.¹⁰

Gliclazide is extensively metabolised in the liver to inactive metabolites. Although CYP2C9 is involved in the metabolism of gliclazide,¹¹ the pharmacokinetics (PK) and pharmacodynamics (PD) of gliclazide seem to be affected mainly by *CYP2C19* genetic polymorphisms.^{12,13}

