Gastrointestinal problems, such as gastroesophageal reflux disease (GERD) are common in T2D.¹⁴ A recent meta-analysis involving 9,067 cases and 81,968 controls showed a significant association between diabetes and the risk of GERD.¹⁵ The prevalence of GERD symptoms in patients with T2D could be as high as 40%.¹⁴ Therefore, millions of individuals are managing blood glucose and GERD concomitantly.¹⁶ Proton pump inhibitors (PPIs) are the medications of choice for GERD, and are primarily metabolised by CYP2C19.¹⁷ The potential for drug-drug interactions is highest for omeprazole and its stereo-isomer esomeprazole, which are metabolised almost entirely by CYP2C19.^{17,18} Furthermore, it has been shown that impact of PPIs on the PK, PD, and therapeutic response to drugs metabolised by CYP2C19 could depend on *CYP2C19* genotype, with highest effect seen in CYP2C19 normal metabolisers (extensive metabolisers, EM)^{19,20} and ultrarapid metabolisers (UM).²¹

Project aims

Considering the high prevalence of use of PPIs,²² the greater incidence of GERD in T2D and likely high concomitant use of PPIs with gliclazide, and the possibility of their interaction via CYP2C19, the primary aim of this pilot clinical study is to explore potential drug-drug interaction between gliclazide and omeprazole in CYP2C19 EM/UM metabolisers. The specific aims are:

1. To explore whether gliclazide PK is altered upon co-administration with omeprazole in healthy volunteers, CYP2C19 EM/UM metabolisers
2. To explore whether gliclazide PD is altered upon co-administration with omeprazole in healthy volunteers, CYP2C19 EM/UM metabolisers

Preliminary data

To our knowledge, there have been no studies exploring potential interaction between any PPI and gliclazide, in animals or humans. To explore this possible drug-drug interaction, we performed preliminary observational analyses in the large population-based GoDARTS study (UK). Briefly, our preliminary data suggest that co-treatment with PPIs, especially omeprazole, increases the risk of hypoglycaemia in patients with CYP2C19 EM/UM phenotype treated with gliclazide. This has been confirmed by better glycaemic response (lower HbA1c) associated with PPI use in EM/UM patients treated with gliclazide. These results support a biologically plausible hypothesis of possible interaction between PPIs and gliclazide, in relation to CYP2C19 genotype.

Study population

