The study protocol will be approved by the Ethics Committee of the General Hospital "Prim. [name]" and the Ethics Committee of the Faculty of Medicine, University of Sarajevo, Sarajevo, Bosnia and Herzegovina (B&H). All procedures will be conducted at the Department of Internal Medicine of the General Hospital in line with the Good Clinical Practice and the Declaration of Helsinki. Prior to inclusion in the study, the nature and purpose of the study will be explained, in both written and verbal form, to each volunteer who will then give the informed written consent to participate in the study.

Volunteers will be initially recruited through advertising by using leaflets, posters and social networks (e.g. Facebook). At least 40 volunteers will be recruited and pre-screened for CYP2C19 genotype. Based on the frequency of CYP2C19*2 variant in B&H population of ~17%,²³ we expect that about two-thirds of screened individuals will be non-carriers of the *2 allele. The recruitment will end when the minimal number of 16 individuals, non-carriers of *2 allele, is reached. Only these individuals (CYP2C19 EM/UM metabolisers) will be included in the drug interaction study after confirmation of their health status.

Inclusion criteria for screening (genotyping)

- Men
- Age 18-30 years
- Non-smokers

Exclusion criteria for screening (genotyping)

- medical history of hepatic, renal, gastrointestinal and hematologic disease or any acute or chronic disease
- any chronic drug therapy
- drug allergy to sulfonylureas and/ or PPIs
- history of drug abuse

Genotyping

Genomic DNA will be extracted from blood samples by using commercial DNA extraction kits. Polymorphisms in the CYP2C19 gene: CYP2C19*2 (rs4244285) and CYP2C19*17 (rs12248560), CYP2C9 gene: CYP2C9*2 (rs1799853), CYP2C9*3 (rs1057910) and a variant in the POR gene encoding a CYP450 redox partner, enzyme P450 oxidoreductase (POR), POR*28 (rs1057868), will be genotyped by specific Drug Metabolism SNP genotyping assays. Genetic test results for CYP2C19 variants will be obtained at the screening, before the randomisation. Only individuals, non-carriers of the CYP2C19*2 allele will be included further in the clinical study. Results obtained for other three variants in the CYP2C9 and POR genes will be used as covariates in the statistical analysis.²⁴

[figure not shown]
Inclusion criteria for drug interaction study

- CYP2C19 normal/ ultrarapid metabolisers (non-carriers of the *CYP2C19**2 allele)

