Treatment

Treatment A: days 1–4, administration of placebo with 240 mL of water
day 5, administration of placebo + 40 mg gliclazide with 240 mL of water

Treatment B: days 1–4, administration of 20 mg omeprazole with 240 mL of water
day 5, administration of 20 mg omeprazole + 40 mg gliclazide with 240 mL of water

*Wash-out period of at least 7 days

Blood collection

Venous blood samples will be collected on day 5 and day 19 for gliclazide, glucose and insulin quantification, through an indwelling intravenous cannula in the arm or by direct venepuncture (in the case of cannula blockage).

A total of 17 blood samples, 5 ml each, will be taken, thus the total blood volume of 85 ml will be taken during 24 hours, which is over 5 times less than the standard 450 ml drawn during voluntary blood donation.

Blood sampling for gliclazide quantification

- gliclazide: pre-dose (0 h), 0.5, 1, 1.5, 2, 2.5, 3, 3.5, 4, 4.5, 5, 6, 7, 8, 10, 12, and 24 h

Blood sampling for glucose and insulin quantification

- glucose: pre-dose (0 h), 0.5, 1, 1.5, 2, 2.5, 3, 3.5, 4, 4.5, 5, 6, 7, 8, 10 and 12 h
- insulin: pre-dose (0 h), 0.5, 1, 1.5, 2, 2.5, 3, 3.5, 4, 4.5, 5, 6, 7, 8, 10 and 12 h

Blood glucose levels will be measured immediately after sampling. Serum samples for insulin and gliclazide quantification will be obtained and stored in properly labelled tubes at -80°C until the analysis.

Gliclazide concentration analysis

Serum gliclazide concentration will be analysed at the Biomarker and Drug Analysis Core Facility, School of Medicine, University of Dundee, by using a stable isotope dilution LC-MS method.

Glucose and insulin quantification

Glucose concentrations will be measured at the laboratory of the General Hospital.

Insulin concentrations will be quantified by enzyme-linked immunosorbent assay (ELISA) using commercially available kit.

Pharmacokinetic analysis

- C_{max} : Gliclazide maximum concentration
- t_{max} : Time to reach C_{max}
- AUC_{0-t} : Area under the concentration–time curve (AUC) up to the last concentration measured
- $\text{AUC}_{0-\infty}$: Area under the concentration–time curve (AUC) extrapolated to infinity
- $t_{1/2}$: Elimination half-life
- $C_{\text{L}/\text{F}}$: Apparent oral clearance
- $V_{\text{d}/\text{F}}$: Apparent volume of distribution

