PK parameters will be calculated by a noncompartmental analysis using PKSolver a program for PK and PD data analysis in Microsoft Excel. Gliclazide maximum concentration (C_{max}) and time to reach C_{max} (t_{max}) will be determined by the inspection of the concentration–time data. The area under the plasma gliclazide concentration–time curve (AUC) up to the last concentration measured (AUC_{0-t}) will be determined using the linear trapezoidal rule. The AUC will be extrapolated to infinity ($\text{AUC}_{t-\infty}$) using C_t/k_{el} , where C_t is the last measured gliclazide concentration and k_{el} is the elimination rate constant that will be estimated from the slope of the best-fit line determined by linear regression analysis of the log-transformed concentration-time curve. The elimination half-life ($t_{1/2}$) will be calculated using the following equation: $t_{1/2}=\ln(2)/k_{\text{el}}$. The apparent oral clearance (CL/F) will be calculated as $\text{dose}/\text{AUC}_{0-\infty}$. The apparent volume of distribution ($V_{\text{d}/\text{F}}$) will be calculated as $\text{dose}/\text{AUC} \times k_{\text{el}}$.

Pharmacodynamic parameters

- C_{\min} : Glucose minimum concentration
- $C_{\text{avg } 0-4}$: Average glucose concentration in the period 0–4 h
- $C_{\text{avg } 0-12}$: Average glucose concentration in the period 0–12 h
- AUC_{0-4} : Area under the glucose concentration–time curve from 0 to 4 h
- AUC_{0-12} : Area under the glucose concentration–time curve from 0 to 12 h

- C_{\min} : Insulin minimum concentration
- $C_{\text{avg } 0-4}$: Average insulin concentration in the period 0–4 h
- $C_{\text{avg } 0-12}$: Average insulin concentration in the period 0–12 h
- AUC_{0-4} : Area under the insulin concentration–time curve from 0 to 4 h
- AUC_{0-12} : Area under the insulin concentration–time curve from 0 to 12 h

To compare the PD effects of gliclazide, the areas under the glucose and insulin concentration–time curve from 0 to 4, and 0 to 12 h after the administration of gliclazide will be calculated using the linear trapezoidal rule. The minimum glucose and insulin concentration will be determined by observation of the concentration–time data, and mean concentrations from 0 to 4 h and from 0 to 12 h will be calculated by dividing the area under the glucose/insulin concentration–time curve by the corresponding time interval.

Safety assessment and precaution measures

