The volunteers will undergo a detailed physical, ECG, and laboratory examination upon inclusion in the drug interaction study. The subjects will be contacted within 14 days of study completion in order to confirm the adequate post-study status.

If any clinical reasons arise that could endanger health status of the subjects by taking blood samples, the blood samples will not be drawn. Considering that bruising, bleeding, infection or pain may occur at the site of venepuncture and cannulation, these procedures will be performed by experienced medical staff to minimise the risk of excessive bleeding or bruising, and a topical anaesthetic may be used, if required, to reduce the pain.

Since this combination of drugs can potentially induce risk of hypoglycaemia, administration of the two drugs will be carried out in the hospital where the subjects will be hospitalised for 24 h and will be continuously under direct medical supervision. In order to avoid the risk of hypoglycaemia, subjects will receive 8 meals (breakfast, lunch, dinner and 5 snacks). In case of any symptom suggestive of hypoglycaemia (nervousness, sweating, intense hunger, trembling, weakness, palpitations), the blood glucose level will be measured using a glucometer and one of the standard measures of raising blood sugar will be applied, such as administration of 20% oral glucose solution, glucose solution for intravenous use, or glucagon for intramuscular use.

In addition, systolic and diastolic blood pressure and heart rate will be measured in the supine position after a 5-minute rest, before drug intake and during the PK profiles at 2, 4, 12 and 24 hours after gliclazide administration.

Power analysis

For identification of clinically relevant drug-drug interaction, we will use the bioequivalence approach. The main outcome to be evaluated is the exposure to gliclazide, expressed as AUC_{0-t} . Sample size calculation was performed using SAS Proc Power procedure for equivalence test in 2x2 crossover design.²⁵ For an equivalence range of 80–125%, the within-subject coefficient of variation for the AUC values for gliclazide of 7.8% based on previous PK studies,^{26,27} and expected test/reference geometric

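### Lack of interaction is tested only on AUC0-t with sampling to 24 h; if omeprazole slows gliclazide elimination, that ratio can understate the change in total exposure, and AUC0-inf has no role in the decision

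*Combined protocol and SAP*

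**What the plan says.** The power analysis section sets the framework: "For identification of clinically relevant drug-drug interaction, we will use the bioequivalence approach". It then names a single metric: "The main outcome to be evaluated is the exposure to gliclazide, expressed as" AUC0-t. The 80–125% range, the CV of 7.8%, the expected ratios of 0.87 to 1.15 and the 85% power with 14 subjects all belong to that calculation.

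The gliclazide sampling schedule ends "6, 7, 8, 10, 12, and 24 h", with nothing between 12 h and 24 h. In the pharmacokinetic analysis section, AUC0-t "will be determined using the linear trapezoidal rule". The elimination rate constant used for extrapolation comes from the "slope of the best-fit line determined by linear regression analysis of the log-transformed concentration-time curve"; which samples enter that line is not stated.

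AUC0-inf, CL/F and half-life are listed and calculated. The statistical analysis section plans geometric means for every PK parameter, and geometric mean ratios with 90% confidence intervals. It gives AUC0-inf no limit and no part in the conclusion.

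On mechanism, the introduction says "the pharmacokinetics (PK) and pharmacodynamics (PD) of gliclazide seem to be affected mainly by" CYP2C19 polymorphisms, and the project aims rest on "the possibility of their interaction via CYP2C19". Under genotyping, only non-carriers of the CYP2C19\*2 "allele will be included further in the clinical study".

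**The concern.** The metric and the hypothesis pull apart. Inhibition of a metabolising enzyme slows elimination and lengthens the tail of the concentration curve. A window that closes at 24 h cuts off more of that tail in the omeprazole period than in the placebo period. The ratio being tested is then pulled towards 1, in the direction of concluding no interaction.

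The plan gives no gliclazide half-life to show that 24 h captures enough of the curve. It also does not say what would be concluded if AUC0-t lay inside 80–125% and AUC0-inf did not, so that choice would be made after seeing the data. The protocol says its results could change practice to prevent hypoglycaemia, which makes a mistaken finding of no interaction the costlier error.

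**Working it through.** **Inputs from the documents.** Limits 80–125%, CV 7.8%, ratios 0.87–1.15, 14 completers, 85% power, 10% drop-out (power analysis); 90% confidence intervals (statistical analysis); the 17 sampling times to 24 h (blood sampling); linear trapezoid (pharmacokinetic analysis).

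**Assumptions not in the documents.** One compartment with first-order absorption, ka 0.6–1.2/h; omeprazole lowers clearance only, with bioavailability, volume and ka unchanged; the 24 h sample is quantifiable in both periods; half-life on placebo varied from 2 to 10 h.

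**1. The plan's own figure.** σw = √ln(1 + 0.078²) = 0.0779. SE of the log ratio = 0.0779 × √(2/14) = 0.0294, with 12 degrees of freedom and t = 1.782. Exact power of the two one-sided tests is 84.7% at a ratio of 1.15 and 85.1% at 0.87, so the stated 85% is reproduced. At a true ratio of 1.25 the pass probability is 5.0%, as it should be. For drop-out, 14/0.9 = 15.6, hence 16. At the expected variance, the largest observed ratio that passes is about exp(0.2231 − 1.782 × 0.0294) = 1.19.

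**2. What truncation does.** In this model AUC0-inf is proportional to 1/k, so replacing k by k/1.25 raises AUC0-inf by exactly 1.25. With f the share of AUC lying before 24 h, the AUC0-24 ratio is 1.25 × f(omeprazole)/f(placebo). Example with a 6 h half-life and ka 1.0/h: f = 0.880 and 0.929, so the ratio is 1.25 × 0.880/0.929 = 1.184. With the planned trapezoid at the protocol times it is 1.175.

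**3. Chance of passing on AUC0-t when the true AUC0-inf ratio is 1.25** (n = 14, CV 7.8%; ranges over ka):

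| Half-life | AUC0-t ratio, planned trapezoid | Pass, planned trapezoid | Pass, exact AUC0-24 |
|---|---|---|---|
| 2 h | 1.26 | 2–3% | about 6% |
| 3 h | 1.24 | 8–10% | 9–10% |
| 4 h | 1.21–1.22 | 21–27% | 18–21% |
| 5 h | 1.19 | 42–49% | 34–38% |
| 6 h | 1.17–1.18 | 62–68% | 53–57% |
| 8 h | 1.14–1.15 | 87–89% | 82–85% |
| 10 h | 1.12–1.13 | 96–97% | 94–95% |

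The last column isolates truncation, which is the main cause. The trapezoid over the 12–24 h gap adds to the effect from about 4 h, is roughly neutral at 3 h and works the other way at 2 h.

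**4. Larger effects, planned trapezoid.** A true ratio of 1.35 passes under 1% of the time at 4 h, 9–13% at 6 h and 40–47% at 8 h. A ratio of 1.5 passes about 0% up to 6 h, 2–4% at 8 h and 17–23% at 10 h. A doubling passes about 0% throughout.

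**5. Power once AUC0-inf must also pass.** The power of the AUC0-inf interval caps that of the two-interval rule. By the formula in step 1, at a ratio of 1.15 with 14 subjects, it is 85% at a CV of 7.8%, 75% at 9% and 67% at 10% (with 16 subjects: 80% at 9% and 73% at 10%). At a ratio of 1.00 it is essentially 100% in each case.

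**The case against.** The strongest reply is that no text says AUC0-t alone decides. The exclusive rule is inferred from the power paragraph, and the statistical analysis section states no pass or fail criterion for any parameter. AUC0-inf, CL/F and half-life will be reported, so a discrepancy would be seen, and the study calls itself an exploratory pilot. This stands in part: what is missing is a decision rule, not an analysis. But the plan adopts the bioequivalence framework and sizes the trial to show lack of interaction, and AUC0-t is the only parameter it connects to that claim.

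Second, the size is undetermined. The pass rate runs from 2% to 97% over the half-lives considered, and the documents do not show which applies. Enrolling only non-carriers of CYP2C19\*2 points, without a number, to the shorter ones. This stands, and limits the weight of the point. So does a related caveat: AUC0-t runs to the last measured concentration, so if some 24 h samples are not quantifiable, the 2–3 h figures are less secure.

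Third, AUC0-t uses observed data only, while AUC0-inf is weakest where the problem is largest. At a true ratio of 1.25 the share beyond 24 h (placebo/omeprazole) is 14–15%/20–21% at 8 h and 20–21%/28–29% at 10 h, and the terminal slope rests on few late samples. That is a reason to require both measures and report the share, not to replace one by the other.

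A reader might infer that the trial is too small, that its test exceeds its 5% level, or that it would miss a large interaction. None of these follows. The sample size reproduces, the level holds for the AUC0-t ratio, and a doubling of exposure is detected at every half-life considered.

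**Conclusion.** The point holds in conditional form. If omeprazole lowers gliclazide clearance without changing absorption, the only metric tied to the 80–125% range understates the rise in total exposure unless the half-life is short. Under the assumptions listed, the effect is small at 3 h or less (at most 10% against a nominal 5%), material from about 4 h and large from about 8 h. It mainly concerns effects near the limit; a ratio of 1.5 is missed with appreciable frequency only beyond about 8 h. Because the documents give no half-life, they do not support saying that the trial will, or probably will, reach a wrong conclusion. They do support saying that the decision rule is exposed to an error in the direction its own hypothesis predicts, and that an already planned parameter could guard against it. This is a cheap improvement rather than a fatal flaw.

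**What to change.** State in both the power analysis and statistical analysis sections that lack of interaction will be concluded only if the 90% confidence intervals for the geometric mean ratios of both AUC0-t and AUC0-inf lie within 80–125%. Report the extrapolated share of AUC0-inf by treatment.

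This needs no new samples and no change in sample size, since AUC0-inf is already calculated. The cost is power near the edge of the range. The plan should restate power at a ratio of 1.15 for the two-interval rule, as below 85% if the AUC0-inf CV exceeds 7.8% (step 5). If there is truly no effect, power is essentially unchanged.

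Simulation with assumed within-subject variation in clearance, absorption and assay error gives two-interval power at 1.15 of roughly 75–87% for half-lives of 2–6 h and 64–81% for 8–10 h. At a true ratio of 1.25 the rule passes in about 2–9% of trials, so it removes most but not quite all of the excess. These simulated figures are illustrative, because the documents do not give the variance components.

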mean ratios between 87–115%, 14 volunteers (7 individuals per sequence) are required to show the lack of interaction with 85% power. To account for potential drop-outs due to non-compliance or loss of follow up (assuming a drop-rate of 10%), a total of 16 subjects, CYP2C19 EM/UM metabolisers, will be randomised. To achieve this number, minimally 40 volunteers will be initially recruited.

Statistical analysis

The geometric mean will be calculated for each PK and PD parameter. Logarithmic transformation will be used for PK variables, except t_{max} , before the analysis. The ratios of the geometric means with 90% confidence intervals (CI) will be assessed by linear mixed models between the two treatment assignments: gliclazide and omeprazole coadministration to that of gliclazide and placebo. The statistical analyses will be performed using the SAS 9.3 software (SAS Institute Inc., Cary, NC).

Original scientific contribution and clinical significance of the research

This research will establish whether omeprazole can alter PK/PD of gliclazide, and thus increase the risk of serious hypoglycaemia with this recommended SU drug.

This study can unravel new, previously unrecognized drug-drug and drug-drug-gene interactions. If clinically relevant alterations in gliclazide PK/PD parameters are established, our findings can lead to changes in clinical practice with the aim of preventing serious, potentially life-threatening hypoglycaemia induced by gliclazide treatment.

Confidentiality and data protection

All clinical, laboratory and genetic data will be processed in a manner designed to protect the identity of the participants, in accordance with the rules of personal data protection and the guidelines of the Good Clinical Practice. Participants' privacy will be respected in all published and other public written data that will result from this study.

Withdrawal from the study

Participants are free to withdraw from the study at any time, without obligation to explain their decision.

Insurance

In accordance with the guidelines of Good Clinical Practice, the subjects will be insured under the terms of insurance for Clinical Trials.

Compensation of costs

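### Does naming only the PK variables in the log-transformation sentence leave the planned PD ratio unobtainable?

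*Combined protocol and SAP*

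**What the plan says.** Three consecutive statements in the Statistical analysis section matter here.

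- Summary measure: "The geometric mean will be calculated for each PK and PD parameter".
- Scale: "Logarithmic transformation will be used for PK variables, except" t_max.
- Comparison: "The ratios of the geometric means with 90% confidence intervals (CI) will be assessed by linear mixed models between the two treatment assignments", with the omeprazole arm set against the placebo arm.

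The Pharmacodynamic parameters section lists five glucose and five insulin measures (minimum, two averages and two areas each). It explains how to calculate them but not on what scale to compare them. The comparison serves the second specific aim under Project aims: "To explore whether gliclazide PD is altered upon co-administration with omeprazole in healthy volunteers, CYP2C19 EM/UM metabolisers". The same section describes the study as a pilot: "the primary aim of this pilot clinical study is to explore potential drug-drug interaction between gliclazide and omeprazole". The Power analysis section puts the weight on a PK measure: "The main outcome to be evaluated is the exposure to gliclazide, expressed as" AUC0–t.

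**The concern.** A linear mixed model gives a ratio of geometric means when it is fitted to log-transformed data and the treatment contrast is exponentiated. Fitted to untransformed data, it gives a difference of arithmetic means. The plan assigns the log step to PK variables and even makes an exception for t_max, so a reader could conclude that leaving out PD was deliberate. The stated rule would then not produce the ratio that the third statement seems to promise for PD.

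Two things would be at stake. Two analysts following the same text could report different PD estimates. And if the scale were left open until the data had been seen, there would be room to choose it across ten PD parameters. PD is one of only two specific aims.

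**Working it through.** **1. Does the gap reach the main outcome or the sample size?** Inputs from Power analysis: equivalence range 80–125%, within-subject CV 7.8%, expected ratio 87–115%, 14 evaluable subjects, 85% power, 10% drop-out. The one-sided level of 0.05 is an assumption, inferred from the 90% interval.

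- σ_w = √ln(1 + CV²) = √ln(1 + 0.078²) = 0.0779.
- SE of the log ratio = σ_w × √(2/N) = 0.0779 × √(2/14) = 0.0294, with N − 2 = 12 degrees of freedom.
- Power of the two one-sided tests, integrated over the distribution of the variance estimate: 0.8505 at a ratio of 0.87 and 0.8468 at 1.15. With N = 12 it is 0.791 and 0.787.
- Drop-out: 14 / (1 − 0.10) = 15.6, rounded up to 16.

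The plan's figures are reproduced. They rest on AUC0–t alone, which is a PK variable and already on the log scale. Nothing decided about PD changes them.

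**2. What does the scale change in principle?** For log-normal data, ratio of arithmetic means = geometric mean ratio × √[(1 + CV_T²)/(1 + CV_R²)], where T is the omeprazole arm and R the placebo arm. With equal CVs the two ratios agree. With a true geometric mean ratio of 1 and assumed CVs of 50% (R) and 70% (T), the factor is √(1.49/1.25) = 1.09; reversed, it is 0.92.

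An invented example without any distribution: placebo values 20, 40, 80 and omeprazole values 30, 50, 90. The arithmetic means are 46.7 and 56.7, so the difference is 10 and the ratio 1.21. The geometric means are 40.0 and 51.3, so the ratio is 1.28. The scales therefore answer different questions, and a report must say which was used.

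**3. Does the text force the wrong scale for PD?** There are two ways to read the comparison sentence.

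- *It covers PD.* The phrase about geometric means then looks back to the first statement, which names PK and PD. The stated estimate fixes the scale, because an untransformed fit would not give the ratio asked for. Two words are missing from the middle sentence, and an analyst would log the PD data.
- *It covers only the variables just said to be log-transformed.* The treatment of t_max supports this reading: it is a listed PK parameter, so it falls under the first statement, yet it is kept off the log scale. The ratios therefore cannot span every parameter in the first statement. On this reading no PD ratio has been promised. Geometric means for PD remain available as descriptive figures, and an untransformed mean difference is a legitimate contrast.

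Neither reading leads to an invalid PD result.

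**The case for a change.** The best argument for a change is that the two readings give different numbers, that the plan does not choose between them, and that the choice can matter. Simulated crossovers with 14 subjects illustrate this. All inputs are assumed, since the documents give no PD variance or distribution.

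- Insulin-like log-normal data (between-subject CV 40/50/60%, within-subject CV 20/25/30%, true ratio 1.25): the scales disagreed on whether the 90% interval excluded no effect in 7.1/13.2/16.1% of trials.
- Glucose-like log-normal data (between-subject CV 10/12/15%, within-subject CV 6/8/10%, true ratio 0.95/0.95/0.92): 2.5/3.6/4.2%.

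What stands is that the PD scale is not written down and that one sentence would settle it. What does not stand is that this harms the trial.

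- The criterion in those simulations is not one the plan uses: it sets no PD margin, hypothesis test or power.
- Across assumed true ratios of 1.0, 1.1, 1.25 and 1.5 in the insulin-like settings, disagreement ran from 0.1% to 16.4%. No simulated trial gave significant results in opposite directions on the two scales.
- Neither scale is better throughout. For insulin-like log-normal data, power was 88/73/60% on the log scale and 84/66/51% on the raw scale. For additive normal data (between-subject SD 30%, within-subject SD 20/25% of the reference mean, true ratio 1.25) it was 89.5/74.8% against 92.9/80.3%. Making the log scale compulsory for PD would not reliably gain precision.

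**Conclusion.** The concern does not call for a change. The plan is silent on the PD scale; it does not contradict itself. The likeliest explanation is a dropped reference to PD in one sentence, which an analyst would supply from the sentences on either side. On the narrower reading, an untransformed comparison is also sound. The effect on the main outcome, the sample size of 14 evaluable and 16 randomised, and the stated power is nil. For the PD aim, the consequence is that the report must state which scale and effect measure were used.

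This conclusion rests on the PD comparison staying exploratory, as Project aims describes it, with no PD margin or formal PD decision. It also assumes that analysts fix the scale before they look at treatment differences, which is ordinary practice.
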